**The use of the Hormone Kisspeptin in *in vitro* fertilisation (IVF) treatment.
Statistical Analysis Plan, version 3.0**

Date: 24/06/2015

MAIN SPONSOR: Imperial College London

FUNDERS: Medical Research Council (MRC)

STUDY COORDINATION CENTRE: Imperial College London

Protocol Code Number ICL/KISS/12/01

EudraCT number 2012-000154-61

Research Ethics Committee (REC) reference: 10/H0707/2

NCT No. NCT01667406

Statistical Analysis Plan, version 3.0

Date: 24/06/2015

Study: One versus 2 doses of kisspeptin (10hrs apart)

Participants will undergo controlled ovarian stimulation using a recombinant FSH/GnRH antagonist protocol and receive either one (Single) or two doses (Double) of kisspeptin-54 (9.6nmol/kg each dose) to trigger oocyte maturation.

On day 2 or 3 of the menstrual cycle, patients will receive daily SC recombinant FSH (recFSH) injections (Gonal F 112.5 IU, Merck Serono, Geneva, Switzerland, administered daily at midday); pelvic ultrasound scan will be performed five days after commencing recFSH, to determine ovarian follicular development. Daily subcutaneous GnRH antagonist injections (Cetrotide 0.25mg, Merck Serono, injected at 9pm daily) will be used to inhibit a premature LH surge, and will be commenced on day 5 of recombinant FSH injections. If serum LH is undetectable (<0.5 IU/L) on Day 7 of recombinant FSH injections, then the dose of cetrotide will be halved to 0.125mg daily. Further ultrasound scans will be performed according to follicular size and response to superovulation. When at least three ovarian follicles \geq 18mm diameter are visible on ultrasound, all patients will receive a subcutaneous bolus injection of kisspeptin-54 administered by a study investigator to trigger oocyte maturation at 36hrs prior to egg collection (between 2030 and 2300h). The dose of kisspeptin-54 will be weight-adjusted (9.6nmol/kg). Patients will then be randomized to receive either a second dose of kisspeptin (9.6nmol/kg), or saline placebo injection at 10hrs following the first kisspeptin trigger injection.

The final dose of GnRH antagonist will be administered 24 hours prior to kisspeptin-54. Serum LH, FSH, oestradiol and progesterone will be measured immediately before, 12hrs and 36hrs after kisspeptin-54 injection, and at the time of egg retrieval in all women. Transvaginal ultrasound-directed oocyte retrieval (TVOR) will be carried out 36h following kisspeptin administration under intravenous anaesthesia (propofol). Intracytoplasmic sperm injection (ICSI) will be performed in all study cycles using sperm from the male partner to allow for assessment of oocyte maturation. All embryos will be graded at day 3 by an independent embryologist, blinded to doses of kisspeptin administered, using the British Fertility Society (BFS) and Association of Clinical Embryologist (ACE) embryo grading scheme for cleavage stage embryos, which describes embryos based on cell number, blastomere size and fragmentation.(30) If at day 3 at least 2 embryos have 6 or more cells, <20% difference in blastomere diameter and <50% fragmentation, they will be incubated until day 5 post oocyte retrieval in order that the strongest embryos can be identified for transfer. At Day 5, embryos will be graded for blastocyst expansion (1 to 6), inner cell mass (A to E) and trophectoderm (A to C).(30) At blastocyst stage, embryos which score at least 3 for blastocyst expansion and A or B for inner cell mass and trophectoderm will be classified as 'high quality embryos'. One or two embryos of highest quality during morphological assessment will be transferred to the uterine cavity 3-5 days following oocyte retrieval.

Assessment of Ovarian Hyperstimulation Syndrome (OHSS)

All women recruited to the study will be regarded as being at high risk of OHSS. Therefore women will be routinely screened for the development of early OHSS (assessed at embryo transfer 3-5days following oocyte retrieval) and late OHSS (assessed 11days following embryo transfer). Women will be screened by symptoms (abdominal pain, abdominal bloating, diarrhoea, nausea, vomiting, subjective reduction in urine output), blood analysis (hemoglobin, hematocrit, white cell count, liver function, renal function, coagulation profile) and ultrasound parameters (ovarian size, presence of free

fluid in pouch of douglas, adnexae, abdomen or pleural cavity). OHSS will be graded according to the criteria of Golan et al. 1989 with updated categorization by Navot et al. 1992.(16,17) OHSS will be independently graded by two experienced IVF clinicians external to the study team ([name] and [name]), who will be provided with blinded data concerning patient symptom, blood analysis and ultrasound parameters. In the event of any discrepancy in categorization of OHSS, the more severe classification will be used.

Study outcomes

The primary outcome is proportion of patients achieving optimal oocyte yield (percentage of mature (metaphase 2; M2) oocytes collected from the number of follicles ≥ 14 mm in size on final ultrasound scan prior to kisspeptin-54 trigger administration of at least 60%). All women will have an ultrasound on the morning of kisspeptin trigger administration. Oocytes will be independently classified as M2 by presence of the first polar body and round ooplasm, by an embryologist blinded to whether one or 2 doses of kisspeptin-54 were administered.

Secondary outcomes are the occurrence of OHSS, fertilization rate (percentage of M2 oocytes which fertilize to form two pronuclear (2PN) zygotes following intracytoplasmic injection with sperm; ICSI), embryo formation and quality, biochemical pregnancy rate (serum β hCG > 10 mIU/mL eleven days after embryo transfer) and clinical pregnancy rate (intrauterine gestational sac with heartbeat on ultrasound at six weeks gestation).

Primary Outcome:

Proportion of patients achieving optimal oocyte yield (defined as proportion of mature eggs collected from follicles of at least 14mm in size on final ultrasound prior to egg collection being at least 60%) (Binary Outcome).

The main covariates to be considered are the number of follicles on final ultrasound scan prior to trigger (follicles ≥ 14 mm on day of trigger), serum AMH, Antral Follicle Count, age, pretrigger estradiol level.

Absolute difference between two groups with CIs will be calculated.

Secondary outcomes:

-Change in reproductive hormones LH, FSH, Estradiol and progesterone from pretrigger values to 4hr, 10hr, 14hr and 20hr values.

Variables to be included in the model: weight, AMH, pretrigger reproductive hormone levels.

Pregnancy (binary) and Implantation rates (ordinal- can be 0, 50 or 100%)-

Baseline covariates which may need adjusting for include age, number of embryos transferred, number of high quality embryos transferred, cause of infertility and BMI.

-Rates of OHSS :

[figure not shown]
Covariates which may need to be adjusted for would include number of follicles >11mm on final ultrasound scan prior to trigger, serum AMH or antral follicle count, number of eggs collected, pretrigger oestradiol level.

List trial data as per CONSORT guidance:

Number of women screened, number who withdrew, number not eligible, number of women recruited and meeting inclusion criteria, but excluded prior to randomisation for complications requiring other IVF treatments prior to receiving kisspeptin eg hydrosalpinx.

We expect to recruit 62 women eligible for randomization (31 per group).

Example:

Tables to be generated following study completion:

Table 1:

Sort by column A	SINGLE	DOIUBLE	BOTH
N	31	31	62
Age (y) C			
Weight (kg) I			
Body mass index (kg/m²) J			
Antral Follicle Count (AFC) F			
Serum AMH* (pmol/L) E			
% with average cycle length \geq35 days D\geq35			
Cause of infertility: G			
PCOS [‡]			
Tubal defect**			
Male Factor [†]			
Mixed			
Idiopathic (unexplained)			
Number of follicles[¶] BF			
Number of Follicles \geq 11mm[¶]			
BK			
Number of Follicles \geq 14mm[¶]			
BN			

Table 1: Baseline characteristics of patients who received kisspeptin-54 trigger. Contains medians (lower quartile, upper quartile) for continuous variables and totals (percentages) for categorical variables.

* AMH = anti-Müllerian hormone

‡ Anovulation due to Polycystic Ovarian Syndrome.

** Blocked or removed Fallopian tubes.

† Infertility is due to a problem with male partner's fertility.

¶ On final ultrasound scan during controlled ovarian stimulation prior to kisspeptin-54 trigger administration.

Table 2:

	SINGLE (n = 31)	DOUBLE (n = 31)	BOTH (n = 62)
Number of Oocytes BZ			
Number of Mature (M2) Oocytes CA			
Oocyte Maturation Rate (%) * CD			
Oocyte Yield (%) † CG			
Proportion achieving ≥60% oocyte yield (%) CH			
Number of 2 pronuclei (2PN) zygotes CE			
Proportion with at Least 4 eggs collected (%) CB			
Fertilization rate (%) ‡ CF			
Number of patients with embryo transfer CN≥1			
Number of Cleaved embryos at day 3 post ICSI CI			
Number of Embryos at day 3 graded as ≥623 CJ			
Number of Patients with day 5 transfer % with CM=5			
Number of Embryos at day 5 CK			
Number of High quality blastocysts (≥3A/B) CL			
Number of High quality blastocysts (>3A/B) transferred CO			
Number of Embryos suitable for freezing CV			
Biochemical Pregnancy rate per protocol (%) CP including those who did not have transfer as 0			
Biochemical Pregnancy rate per transfer (%) CP not including those who did not have transfer			
Clinical Pregnancy rate per protocol (%) CQ			

including those who did not have transfer as 0

Clinical Pregnancy rate per transfer (%) CQ
not including those who did not have transfer

Implantation rate (%) Ψ CU

Live Birth rate per protocol (%)

Table 2: IVF outcome measures following kisspeptin-54 trigger. Contains means (standard deviation) for continuous variables and totals (percentages of N) for categorical variables

* Oocyte Maturation Rate is the percentage of oocytes collected which were mature.

† Oocyte Yield is the percentage of mature oocytes collected from the number of follicles

≥ 14 mm in diameter on the final ultrasound scan prior to kisspeptin-54 trigger administration.

‡ Fertilization rate is the percentage of mature oocytes which fertilize following intracytoplasmic injection with sperm (ICSI).

Ψ Implantation rate is defined as the percentage of embryos transferred which implant on assessment by ultrasound at 6 weeks of gestation.

Table 3:

Kisspeptin-54 Dose	SINGLE		DOUBLE	BOTH	
	N	31	31		
At least 1 oocyte retrieved BZ\geq1					
At least 1 mature oocyte retrieved CA\geq1					
At least 1 2PN zygote formed \ddagger CE\geq1					
Segmentation Ψ					
Number of patients with embryo transfer CN\geq1					
Number of patients with day 5 transfer* % with CM=5					
High quality embryo transfer\dagger CO\geq1					
Biochemical pregnancy at 11 days CP					
Clinical pregnancy at 6 weeks CQ					
Miscarriage / Still Birth (PENDING)					
Live Birth (PENDING)					

Table 3: Summary of patient response following kisspeptin-54 triggering.

The number of patients completing each criterion is shown (% in brackets).

\ddagger 2PN is two pronuclear zygote assessed on day following oocyte retrieval

Ψ Segmentation refers to cryopreservation of all embryos and embryo transfer in a subsequent frozen cycle due to high risk of OHSS

* Embryo transfer on day 5

\dagger Transfer of at least one high quality embryo. High quality embryos were blastocyst embryos graded on day 5 as being at least 3A or B in quality (Gardner et al. 2000).

Table 4:

	Early OHSS By single vs double	Late OHSS By single by double
OHSS Symptomatology		
Number of patients screened by OHSS symptoms		
At least 1 symptom potentially consistent with OHSS		
Number of patients requiring medical intervention or hospitalization for OHSS		
Sonographical Screening		
Number of patients screened with pelvic ultrasound		
Mean ovarian volume (mls)		
Increase in ovarian volume as proportion of baseline scan		
Max ovarian diameter (mm)		
Number of patients with maximum ovarian diameter >5cm		
Number of patients with maximum ovarian diameter >8cm		
Number of patients with pleural effusion		
Number of patients with free fluid in abdomen		
Number of patients with fluid in POD / adnexa		
Blood parameters		
Number of patients screened with Blood analysis		
Number of patients with Hematocrit >45%		
Number of patients with White Cell Count >15 x10 ⁹ /L		
Number of patients with ALT or AST >2xULN		
Number of patients with total protein >80 g/L		
Number of patient with creatinine >110 µmol/L		

Number of patients with OHSS ¥

Normal

Mild

Moderate

Severe

Critical

Table 4: OHSS in high risk women following kisspeptin-54 trigger

¥ Diagnosis of OHSS was performed by two experienced IVF physicians independent of the study team provided with blinded data according to the criteria of Golan et al. 1989 with updated categorization of severe and critical OHSS by Navot et al. 1992.(16,17)

POD, Pouch of douglas; ALT, Alanine transaminase; AST, Aspartate transaminase; ULN, Upper Limit of Normal.

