7.3 REPORTING PROCEDURES

All adverse events will be reported. Depending on the nature of the event the reporting procedures below will be followed. A flowchart is given below to aid in the reporting procedures.

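### OHSS is graded from two scheduled screens 11 days apart, and events recorded outside them are not routed to the graders, so the graded rate may understate occurrence

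*SAP*

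**What the plan says.** The SAP (Study outcomes) states: "Secondary outcomes are the occurrence of OHSS". Protocol section 3.1 lists rates of OHSS among the secondary outcomes.

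The SAP section on assessment of OHSS sets two screens: "early OHSS (assessed at embryo transfer 3-5days following oocyte retrieval) and late OHSS (assessed 11days following embryo transfer"). On content it says: "Women will be screened by symptoms (abdominal pain, abdominal bloating, diarrhoea, nausea, vomiting, subjective reduction in urine output), blood analysis", followed by ultrasound findings. Two clinicians outside the study team do the grading, "who will be provided with blinded data concerning patient symptom, blood analysis and ultrasound parameters". When they differ, the rule is: "In the event of any discrepancy in categorization of OHSS, the more severe classification will be used".

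Table 4 of the SAP has an early and a late column, each split by single and double dose, with counts from Normal to Critical. It also has a row headed "Number of patients requiring medical intervention or hospitalization for OHSS".

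Safety reporting in the protocol is not tied to these two visits. Section 7.3 says "All adverse events will be reported", and section 7.1 makes any admission to hospital a serious adverse event.

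**The concern.** The outcome is worded as occurrence, which covers the whole period at risk. The grades come from data gathered at two scheduled assessments. The SAP does not connect the two: it has no symptom recall period, no unscheduled OHSS assessment and no rule for an episode that arises and settles between screens.

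Take a woman with a fresh transfer who becomes unwell on day 8 after retrieval, is treated, and has recovered by day 15. She would be in the adverse-event record and should be counted in Table 4's intervention row. Yet she could be graded Normal in both columns, because her blood results and scan from day 8 have no stated route to the graders. The safety table could then show a treated case with no grade to match.

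This matters because avoiding OHSS is the protocol's reason for replacing hCG (sections 1.1 and 1.2). The protocol quotes background OHSS per IVF cycle, and a rate taken from two screens is not directly comparable with a per-cycle figure.

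**Working it through.** The plan states no figure for this point, so there is none to reproduce. The check has three steps.

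**1. Timing (SAP, assessment of OHSS).** The early screen is at transfer, day 3 to 5 after retrieval. The late screen is 11 days after transfer: 3 + 11 = 14 and 5 + 11 = 16, so day 14 to 16. The gap is 11 days. This applies to women who have a fresh transfer, since both screens are dated from it.

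**2. What reaches the grade.**

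| Source | Captured outside the two screens? | Stated to reach the graders? |
|---|---|---|
| Symptoms at screening (SAP) | Not stated; no recall period | Yes |
| Blood tests and ultrasound at screening (SAP) | No | Yes |
| Intervention or admission for OHSS (SAP, Table 4) | Row not confined to visit-day findings | No |
| Adverse events and SAEs (protocol 7.1, 7.3) | Yes | No |

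The rule that the more severe grade prevails settles disagreement between graders on the same data. It does not reach events that the graders never see.

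**3. Direction and illustrative size.** An episode that is not seen can only lower the graded count. To show the mechanism, suppose that onset is uniform over the 11-day gap, the episode lasts D days, symptoms reflect the visit day only, no residual finding remains, and nothing else reaches the graders. Then

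P(absent at both screens) = (11 − D)/11

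- D = 3: 8/11 = 73%
- D = 5: 6/11 = 55%
- D = 7: 4/11 = 36%
- D of 11 or more: 0%

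If p is the true rate and s the share of episodes that start in the gap, the observed rate is p × [1 − s(11 − D)/11]. The documents give neither D nor s. I assume D of 3 to 7 days and s of 10% to 50%. The missed share then runs from 0.10 × 4/11 = 3.6% to 0.50 × 8/11 = 36.4%. The background rates come from protocol section 1.2 and the 62 women from the SAP; both serve for illustration only.

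| True rate | Observed rate | Women missed of 62 |
|---|---|---|
| 1 in 3 (mild) | 32.1% to 21.2% | 0.75 to 7.5 |
| 1 in 10 (moderate or severe) | 9.6% to 6.4% | 0.2 to 2.3 |

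For each assumed D and s these are upper limits on the loss, because recalled symptoms, residual scan or blood findings, or informal forwarding of records would all reduce it. With 31 women per arm, one ungraded case is 1/31 = 3.2 percentage points in that arm.

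**The case against.** The strongest reply is that the SAP never says OHSS is a visit-day status. It screens for the development of early and late OHSS, and symptoms are part of what is graded. If women are asked about symptoms since the last visit, which the text allows, the graders would learn of an illness on day 8. This stands, and it rules out saying that such an episode is graded Normal. It does not close the gap, because the blood results and scan still belong to the screening visit and recalled symptoms cannot supply the findings at the peak of an episode.

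Second, the serious cases are not lost. Those needing intervention or admission have their own row in Table 4, and adverse events and SAEs are reported throughout. This also stands. A treated woman may lack a severity grade, but she is not missing from the safety data. Milder, untreated episodes are the ones most exposed.

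Third, a reader might infer from Table 4 that the plan has no per-woman OHSS total. That is unsafe. A figure directly under the rates-of-OHSS item in the SAP is not shown in the text available and may define the combined outcome. The covariates listed there are measured per woman, and the tables are introduced as examples.

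Fourth, both arms have the same schedule and the graders receive blinded data, so nothing shows bias in the randomised comparison. Two screens with two external graders is a reasonable base.

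**Conclusion.** The point holds as a gap in how the outcome is defined and in what the graders receive. As written, an OHSS episode outside the two screens may go without a severity grade, or be graded Normal, while appearing elsewhere in the safety record. The graded rate may then understate occurrence, and any such error is downward.

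A reader might go further and conclude that OHSS is measured as point prevalence and that its rate is understated by a known amount. The documents do not support that. They are silent on symptom recall, and they give no episode duration or onset pattern. The figures in the working rest on assumed values, and the loss falls to zero for episodes that start in the gap and last 11 days or more. Nor do the documents show bias between single and double dosing.

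OHSS is a secondary outcome but central to the trial's rationale, and the remedy is cheap, so the change is worth making.

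**What to change.** In the SAP:

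- Define the OHSS outcome as each woman's worst grade from trigger to the late screen.
- State that symptoms at each screen are asked for the period since the previous assessment.
- Give the two external graders blinded data from any unscheduled visit, admission or adverse-event report in that window, as well as the two screens.
- Add to Table 4 one per-woman summary by arm, any OHSS by worst grade, beside the early and late columns, unless the figure not shown under the rates-of-OHSS item already defines it.

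The cost is SAP wording, one table column, and the work of blinding and forwarding records that protocol section 7.3 already requires. The graders are already part of the plan, and no visit is added. The downside is that the reported OHSS rate may rise slightly.

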6. TREATMENTS

6.1 TREATMENT ARMS

All of the women in this study will undergo a standard FSH/GnRH antagonist IVF protocol with luteal phase supplementation which is used for women undergoing IVF treatment at Hammersmith Hospital under the supervision of [name] (Director of the IVF Unit) (please see appendix 2). The only difference will be that women taking part in the study will have either one or two subcutaneous injections of kisspeptin in place of hCG in order to trigger oocyte maturation. This injection will be administered by two experienced physicians at the Hammersmith Hospital or in the participant's home according to the patients preference.

The patients will be administered with the first dose of kisspeptin 12-24 hours after the last injection of FSH/GnRH antagonist for final oocyte maturation. Women will be randomised to receive either a single dose of kisspeptin (9.6nmol/kg), or two doses of kisspeptin 8-12 hours apart. The optimal dosing regimen of kisspeptin will be the dose of kisspeptin which causes the highest level of oocyte maturation.

Since kisspeptin causes a rapid and potent rise in LH release following sc injection we would expect that kisspeptin will induce oocyte maturation at a similar timing as when hCG or GnRH are used to trigger oocyte maturation which is 32-36 hours after injection (13, 16, 17, 18). In order to determine the changes in reproductive hormones which occur during oocyte maturation, participants will be given two options for blood testing following injection of kisspeptin. These options will be discussed at screening, and participants are entirely free to decline overnight blood sampling without altering their study participation or clinical care:

Option 1. Overnight blood sampling: Participants opting for overnight blood sampling will be admitted to the Wellcome / NIHR Clinical Research Facility (CRF), Hammersmith Hospital. Blood will be sampled for measurement of plasma LH, FSH, progesterone, kisspeptin and oestradiol. Total blood loss will not exceed 100ml, and blood sampling will not be performed more frequently than every 15min.

Option 2. Less intensive blood testing: In participants who do not opt into overnight blood sampling, plasma LH, FSH, progesterone and oestradiol will be measured immediately before kisspeptin injection, on up to six occasions within the first 24h following kisspeptin injection (according to participant availability), and then at the time of oocyte retrieval.

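### The SAP analyses hormone change at 4, 10, 14 and 20 h, but none of these times is in its all-women sampling schedule, and the scheduled 12 h sample goes unused

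*SAP*

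**What the plan says.** **Analysis times.** Under its Secondary outcomes heading the SAP lists "Change in reproductive hormones LH, FSH, Estradiol and progesterone from pretrigger values to 4hr, 10hr, 14hr and 20hr values". For the model it gives only covariates: "Variables to be included in the model: weight, AMH, pretrigger reproductive hormone levels". It names no between-arm contrast and no principal time.

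**Sampling times.** In the study description the SAP says that the same four hormones "will be measured immediately before, 12hrs and 36hrs after kisspeptin-54 injection, and at the time of egg retrieval in all women". Oocyte retrieval "will be carried out 36h following kisspeptin administration", so the retrieval sample and the 36 h sample share one time.

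**Randomised comparison.** The title line reads "Study: One versus 2 doses of kisspeptin (10hrs apart)". All women receive the first injection of kisspeptin. They are then randomised to a second dose or a "saline placebo injection at 10hrs following the first kisspeptin trigger injection". On numbers: "We expect to recruit 62 women eligible for randomization (31 per group)".

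**Protocol sampling.** Protocol 6.1 offers two options. One is overnight admission, which women may decline. The other is a draw before the injection, up to six draws in the first 24 h as the woman's availability allows, and one at retrieval. Of these it says "These options will be discussed at screening". Appendix 1 also gives a maximum of six draws in 24 h plus retrieval. Neither place names 4, 10, 14 or 20 h. The sensitivity analysis in Protocol 8.1 and 9 is for drop-outs; missed blood draws are not mentioned.

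**The concern.** The SAP gives two lists of times for the same four hormones, and they share only the pre-trigger baseline. An analyst working from the SAP would find no all-women sample at any listed time, and two all-women samples with no analysis assigned to them.

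What is at stake is which women, and which times, carry the hormone comparison of one dose with two. If the four listed times come only from optional or availability-based draws, the result describes a subset that the plan does not define. If the times and the contrast stay open, they can be settled after the data are seen. The 12 h sample is both planned for everyone and later than the randomised injection, yet it has no role in the listed analysis.

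LH, FSH and estradiol are secondary outcomes in Protocol 3.1, and the trial's rationale runs through the LH surge, so the point is worth settling. The primary outcome, oocyte yield, does not depend on it.

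**Working it through.** The plan gives no figure to reproduce here. The check compares the lists of times and places each time relative to the second injection. Times are counted from the first injection, as the SAP does when it sets the trigger 36 h before retrieval.

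**Step 1: overlap of the lists**
- Analysed post-trigger times (SAP, Secondary outcomes): {4, 10, 14, 20} h.
- All-women post-trigger times (SAP, study description): {12, 36} h, with retrieval = 36 h.
- Analysed times that are scheduled for all women: 0 of 4.
- Scheduled post-trigger times that are analysed: 0 of 2.

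**Step 2: position relative to the second injection**

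Offset = sample time − injection time. The SAP fixes the injection at 10 h; Protocol 6.1 allows 8 to 12 h.

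| Sample | Listed for analysis | Planned for all women | Offset, SAP (10 h) | Offset, protocol window (12 h to 8 h) |
|---|---|---|---|---|
| 4 h | yes | no | −6 h | −8 to −4 h |
| 10 h | yes | no | 0 h | −2 to +2 h |
| 12 h | no | yes | +2 h | 0 to +4 h |
| 14 h | yes | no | +4 h | +2 to +6 h |
| 20 h | yes | no | +10 h | +8 to +12 h |
| 36 h | no | yes | +26 h | +24 to +28 h |

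At 4 h both arms have had the same treatment under either document, so an arm difference there cannot be an effect of the second dose. At 10 h the answer depends on whether the draw or the injection comes first, which the SAP does not say. The 12, 14 and 20 h samples all follow the injection at the SAP's 10 h. At the far end of the protocol window the 12 h sample would coincide with it.

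**Step 3: can protocol sampling supply the listed times?**
- All four times fall within 24 h. Adding the 12 h draw gives 4, 10, 12, 14 and 20 h, which is five draws against a maximum of six.
- The SAP gives the first injection between 2030 and 2300 h, so the 4 h draw falls between 0030 and 0300 h. Women may decline overnight sampling.
- Protocol sampling can therefore supply these times in some women but does not secure them in all. The documents do not say how many of the 62 would contribute.

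**The case against.** The strongest reply is that the SAP says what is measured in all women, not that nothing else is measured. Read with the protocol, the likeliest intention is a core schedule plus the protocol's more intensive sampling, poorly cross-referenced. This stands in part. A reader might infer that the hormone analysis has no data, and the documents do not support that. What remains is that neither document fixes the four times or says who contributes.

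A second reply is that the SAP never claims the 4 h value tests the second dose. That is fair: Protocol 6.1 wants the time course of the LH surge, and 4 h and 10 h are proper data for it. A reader might count the pre-injection hormone-by-time results as wasted comparisons. The SAP assigns no between-arm contrast to those times, so such a count would not measure an error.

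Third, a reader might put a figure on lost precision. That needs the fraction of women sampled at each time, which the documents do not give.

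Fourth, one might argue that because the options are discussed at screening, who contributes cannot depend on arm. That goes too far. Availability-based attendance at 14 h and 20 h is settled after the second injection. The saline injection, and telling women that it may be either (Protocol 5.2), make arm-driven attendance less likely, but the same section calls the trial open label. Arm-related selection is neither shown nor excluded.

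Finally, the SAP's prose summary of secondary outcomes omits hormones, and no table shell covers them. That limits the weight of the point but does not reconcile the lists.

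**Conclusion.** The point holds as a contradiction between two stated lists in the SAP. None of the four analysed times is scheduled for all women, and neither all-women post-trigger sample is analysed. No text reconciles them. As written, the hormone analysis would rest on an unspecified subset of the 62 women, with the one-versus-two-dose contrast undefined and the all-women 12 h sample unused.

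This rests on counting times from the first injection and on the SAP's 10 h second injection. Under the protocol's 8 to 12 h window the overlap result does not change; only the positions of the 10 h and 12 h samples around the injection do.

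The size is modest: one secondary outcome, with the primary outcome untouched. The change should be made, but the trial's main conclusion does not depend on it. The documents do not show missing data, a quantified loss of precision, or bias between arms.

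**What to change.** In SAP wording:

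1. Reconcile the sampling paragraph and the hormone outcome with Protocol 6.1 and Appendix 1. Mark which times are planned for all women and which come only from optional or availability-based draws.
2. Base the one-versus-two-dose hormone comparison on samples taken after the second injection: the all-women 12 h sample, plus 14 h and 20 h where available. Adjust for weight, AMH and the pre-trigger value, as the SAP already lists. Report 4 h descriptively, and 10 h likewise if it is drawn before the injection.
3. State the actual order of the 10 h draw and the second injection, and record actual draw and injection times. The documents do not give this order, so it must come from the trial's procedures.
4. Report the number of women sampled per arm at each time.

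**Cost.** Slightly more analysis work, and fewer women at the times that stay optional. Sample size does not change, and no draws are added beyond the six the protocol allows in 24 h. That count does not show that night-time draws are feasible in all women, so wording alone is enough only if those times remain optional.
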